14.1 Table 1: Baseline characteristics before and after adjustment

Variable	Before adjustment			After adjustment		
	Referent	Exposure	Std. diff.	Referent	Exposure	Std. diff.
Number of patients			-			-
Age categories						
...						

14.2 Table 2: Follow-up time

Patient Group	Median Follow-Up Time (Days) [IQR]
Overall Patient Population	
Referent	
Exposure	

14.3 Table 3: Censoring events

	Overall	Referent	Exposure

Outcome			
Death			
Start of an additional exposure			
End of index exposure			
Specified date reached			
End of patient data			
End of patient enrollment			
...			

14.4 Table 4: Results from primary analyses;

Analysis	No. exposed events	No. referent events	Exposed rate	Referent rate	HR (95% CI)
Crude					
Analysis 1					
Analysis 2					
...					

HR, Hazard Ratio; CI, Confidence Interval.

14.5 Table 5: Results from secondary analyses;

15. References

Appendix A

Trial Name (with web links)	EINSTEIN PE
Trial Name (with pdf links)	EINSTEIN PE
NCT	NCT00439777
Therapeutic Area	Cardiology/Vascular Diseases
Study batch	NOACs
Brand Name	Xarelto
Generic Name	Rivaroxaban
Sponsor	Bayer Johnson & Johnson Pharmaceutical Research & Development, L.L.C
Year	2012
Measurable endpoint	Percentage of Participants With Symptomatic Recurrent Venous Thromboembolism [VTE] (i.e. the Composite of Recurrent Deep Vein Thrombosis [DVT] or Fatal or Non-fatal Pulmonary Embolism [PE]) Until the Intended End of Study Treatment
Exposure	Rivaroxaban
Comparator	Enoxaparin/VKA
Population	Patients of legal age who had acute symptomatic pulmonary embolism with or without deep-vein thrombosis
Trial finding	HR = 1.12 (95% CI 0.75 to 1.68)
No. of Patients	4,832 (2,419 in exposed arm)
Non-inferiority margin	HR = 2.0
Assay Sens. Endpoint (from trial)	Percentage of Participants With the Composite Variable Comprising Recurrent DVT, Non-fatal PE and All Cause Mortality Until the Intended End of Study Treatment
Finding for potential Assay Sens. Outcome from trial-	HR = 0.85 (95% CI 0.63 to 1.14)
Power	0.90. Assuming equal efficacy, a total of 88 events was calculated to give a power of 90% to prove that rivaroxaban is at least as effective as the comparator, considering a non-inferiority upper CI margin for the hazard ratio of 2.0 (two-sided $\alpha=0.05$). A mean incidence for the primary efficacy outcome of 3% was expected and an enrollment of at least 3000 patients was necessary

Appendix A

Title

Venous Thromboembolism (VTE)

ICD-9 Dx inpatient primary position

PE

- 415.1 PULMONARY EMBOLISM AND INFARCTION
- 415.11 IATROGENIC PULMONARY EMBOLISM AND INFARCTION
- 415.19 OTHER PULMONARY EMBOLISM AND INFARCTION

DVT

- 451.1 PHLEBITIS AND THROMBOPHLEBITIS OF DEEP VEINS OF LOWER EXTREMITIES
- 451.11 PHLEBITIS AND THROMBOPHLEBITIS OF FEMORAL VEIN (DEEP) (SUPERFICIAL)
- 451.19 PHLEBITIS AND THROMBOPHLEBITIS OF OTHER
- 451.2 PHLEBITIS AND THROMBOPHLEBITIS OF LOWER EXTREMITIES UNSPECIFIED
- 451.81 PHLEBITIS AND THROMBOPHLEBITIS OF ILIAC VEIN
- 451.9 PHLEBITIS AND THROMBOPHLEBITIS OF UNSPECIFIED SITE
- 453 BUDD-CHIARI SYNDROME
- 453.1 THROMBOPHLEBITIS MIGRANS
- 453.2 EMBOLISM AND THROMBOSIS OF INFERIOR VENA CAVA
- 453.4 ACUTE VENOUS EMBOLISM AND THROMBOSIS OF DEEP VESSELS OF LOWER EXTREMITY
- 453.4 ACUTE VENOUS EMBOLISM AND THROMBOSIS OF UNSPECIFIED DEEP VESSELS OF LOWER EXTREMITY
- 453.41 ACUTE VENOUS EMBOLISM AND THROMBOSIS OF DEEP VESSELS OF PROXIMAL LOWER EXTREMITY
- 453.42 ACUTE VENOUS EMBOLISM AND THROMBOSIS OF DEEP VESSELS OF DISTAL LOWER EXTREMITY
- 453.5 CHRONIC VENOUS EMBOLISM AND THROMBOSIS OF DEEP VESSELS OF LOWER EXTREMITY
- 453.5 CHRONIC VENOUS EMBOLISM AND THROMBOSIS OF UNSPECIFIED DEEP VESSELS OF LOWER EXTREMITY
- 453.51 CHRONIC VENOUS EMBOLISM AND THROMBOSIS OF DEEP VESSELS OF PROXIMAL LOWER EXTREMITY
- 453.52 CHRONIC VENOUS EMBOLISM AND THROMBOSIS OF DEEP VESSELS OF DISTAL LOWER EXTREMITY
- 453.8 ACUTE VENOUS EMBOLISM AND THROMBOSIS OF OTHER SPECIFIED VEINS
- 453.82 ACUTE VENOUS EMBOLISM AND THROMBOSIS OF DEEP VEINS OF UPPER EXTREMITY
- 453.83 ACUTE VENOUS EMBOLISM AND THROMBOSIS OF UPPER EXTREMITY UNSPECIFIED
- 453.84 ACUTE VENOUS EMBOLISM AND THROMBOSIS OF AXILLARY VEINS
- 453.85 ACUTE VENOUS EMBOLISM AND THROMBOSIS OF SUBCLAVIAN VEINS
- 453.86 ACUTE VENOUS EMBOLISM AND THROMBOSIS OF INTERNAL JUGULAR VEINS
- 453.87 ACUTE VENOUS EMBOLISM AND THROMBOSIS OF OTHER THORACIC VEINS
- 453.89 ACUTE VENOUS EMBOLISM AND THROMBOSIS OF OTHER SPECIFIED VEINS

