1.3 Primary endpoint for replication

The primary outcome of the study was symptomatic, recurrent VTE

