Appendix A

I80.232	Phlebitis and thrombophlebitis of left tibial vein
I80.233	Phlebitis and thrombophlebitis of tibial vein, bilateral
I80.239	Phlebitis and thrombophlebitis of unspecified tibial vein
I80.29	Phlebitis and thrombophlebitis of other deep vessels of lower extremities
I80.291	Phlebitis and thrombophlebitis of other deep vessels of right lower extremity
I80.292	Phlebitis and thrombophlebitis of other deep vessels of left lower extremity
I80.293	Phlebitis and thrombophlebitis of other deep vessels of lower extremity, bilateral
I80.299	Phlebitis and thrombophlebitis of other deep vessels of unspecified lower extremity
I80.3	Phlebitis and thrombophlebitis of lower extremities, unspecified
I80.9	Phlebitis and thrombophlebitis of unspecified site
I82.0	Budd-Chiari syndrome
I82.1	Thrombophlebitis migrans
I80.3	Phlebitis and thrombophlebitis of lower extremities, unspecified
I82.4	Acute embolism and thrombosis of deep veins of lower extremity
I82.40	Acute embolism and thrombosis of unspecified deep veins of lower extremity
I82.401	Acute embolism and thrombosis of unspecified deep veins of right lower extremity
I82.402	Acute embolism and thrombosis of unspecified deep veins of left lower extremity
I82.403	Acute embolism and thrombosis of unspecified deep veins of lower extremity, bilateral
I82.409	Acute embolism and thrombosis of unspecified deep veins of unspecified lower extremity
I82.41	Acute embolism and thrombosis of femoral vein
I82.411	Acute embolism and thrombosis of right femoral vein
I82.412	Acute embolism and thrombosis of left femoral vein
I82.413	Acute embolism and thrombosis of femoral vein, bilateral
I82.419	Acute embolism and thrombosis of unspecified femoral vein
I82.42	Acute embolism and thrombosis of iliac vein
I82.421	Acute embolism and thrombosis of right iliac vein
I82.422	Acute embolism and thrombosis of left iliac vein
I82.423	Acute embolism and thrombosis of iliac vein, bilateral
I82.429	Acute embolism and thrombosis of unspecified iliac vein
I82.43	Acute embolism and thrombosis of popliteal vein
I82.431	Acute embolism and thrombosis of right popliteal vein
I82.432	Acute embolism and thrombosis of left popliteal vein
I82.433	Acute embolism and thrombosis of popliteal vein, bilateral
I82.439	Acute embolism and thrombosis of unspecified popliteal vein
I82.44	Acute embolism and thrombosis of tibial vein

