Appendix A

I82.629	Acute embolism and thrombosis of deep veins of unspecified upper extremity
I82.890	Acute embolism and thrombosis of other specified veins
I82.90	Acute embolism and thrombosis of unspecified vein
I82.A1	Acute embolism and thrombosis of axillary vein
I82.A11	Acute embolism and thrombosis of right axillary vein
I82.A12	Acute embolism and thrombosis of left axillary vein
I82.A13	Acute embolism and thrombosis of axillary vein, bilateral
I82.A19	Acute embolism and thrombosis of unspecified axillary vein
I82.B1	Acute embolism and thrombosis of subclavian vein
I82.B11	Acute embolism and thrombosis of right subclavian vein
I82.B12	Acute embolism and thrombosis of left subclavian vein
I82.B13	Acute embolism and thrombosis of subclavian vein, bilateral
I82.B19	Acute embolism and thrombosis of unspecified subclavian vein
I82.C1	Acute embolism and thrombosis of internal jugular vein
I82.C11	Acute embolism and thrombosis of right internal jugular vein
I82.C12	Acute embolism and thrombosis of left internal jugular vein
I82.C13	Acute embolism and thrombosis of internal jugular vein, bilateral
I82.C19	Acute embolism and thrombosis of unspecified internal jugular vein

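### The DVT block of the primary-outcome code list counts Budd-Chiari syndrome and thrombophlebitis migrans as recurrent VTE, and no narrower sensitivity outcome tests the unspecified and other-vein codes

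*Combined protocol and SAP*

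**What the plan says.** Section 1.3 takes the primary endpoint from the trial: "The primary outcome of the study was symptomatic, recurrent VTE". The measurable-endpoint row of Appendix A spells out that outcome as "the Composite of Recurrent Deep Vein Thrombosis [DVT] or Fatal or Non-fatal Pulmonary Embolism [PE". Section 6.3.1 names the study outcome only as VTE and refers to Appendix A, so the code list there is the working definition.

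The list is headed "ICD-9 Dx inpatient primary position", with a matching heading for ICD-10, and splits into a PE block and a DVT block. The DVT block includes:

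- "453 BUDD-CHIARI SYNDROME" and "453.1 THROMBOPHLEBITIS MIGRANS", repeated in ICD-10 as I82.0 and I82.1.
- Unspecified-site codes such as 451.9 ("PHLEBITIS AND THROMBOPHLEBITIS OF UNSPECIFIED SITE"), with 451.2, 453.83, 453.9, I80.3, I80.9, I82.60 and I82.601 to I82.609, and I82.90.
- Other-vein codes: 453.8 and 453.89, and I82.890 ("Acute embolism and thrombosis of other specified veins").

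No rationale or validation figure is given for these codes. Section 13.2, on sensitivity analyses, has a heading and no entries.

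**The concern.** The list is broader than the composite it stands in for. A hepatic-vein syndrome and a migratory phlebitis are filed as DVT, and several further labels name neither a site nor a depth that would establish a deep vein. The list itself draws that distinction: it separates deep upper-extremity veins (453.82, I82.62) from unspecified ones (453.83, I82.60).

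This matters because the study is judged by non-inferiority against a hazard ratio of 2.0. In a superiority comparison, events indifferent to the drug contrast usually work against the claim being made. Here they would work in its favour, by moving the estimate toward 1 and away from the margin. They would also blur the comparison with the trial's result, which was obtained on the narrower composite.

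**Working it through.** **Count of codes.** The ICD-9 DVT block has 26 printed lines. Eight are in question: 451.2, 451.9, 453, 453.1, 453.8, 453.83, 453.89 and 453.9. In ICD-10, 11 distinct codes are in question: I80.3, I80.9, I82.0, I82.1, I82.60, I82.601, I82.602, I82.603, I82.609, I82.890 and I82.90. Only four of these 19 are clear mismatches by label: 453, 453.1, I82.0 and I82.1. The other 15 are ambiguous.

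**Inputs from Section 10 (pooled).** 32,998 matched patients in 1:1 pairs, risk 13.87 per 1,000, assumed HR 1.12, margin 2, two-sided alpha 0.05.

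**The plan's own figure.** Expected events E = 32,998 × 13.87/1,000 = 457.68, as printed. Power = Φ(√(E/4) × [ln 2 − ln 1.12] − 1.96) = Φ(10.70 × 0.5798 − 1.96) = 0.999989, which matches the printed 0.999988934. The same formula returns the other Section 10 powers: Optum 0.5947, MarketScan 0.9647, Medicare 0.9932.

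**Dilution.** Let f be the share of reference-arm events that are not DVT or PE, and h the hazard ratio for those events. Then

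observed HR = (1 − f) × true HR + f × h.

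If h equals the true HR, nothing changes. If the extra events are indifferent to the choice of drug, h = 1. The table uses h = 1. The documents give no value for f, so its range is an assumption. The error column is Φ(√(E/4) × ln(2/observed HR) − 1.96) with E = 457.68.

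| Assumed f | Observed HR if true HR is 1.12 | Observed HR if true HR is 2.0 | Chance of wrongly declaring non-inferiority at true HR 2.0 |
|---|---|---|---|
| 0 | 1.120 | 2.00 | 2.5% |
| 1% | 1.119 | 1.99 | 2.8% |
| 2% | 1.118 | 1.98 | 3.2% |
| 5% | 1.114 | 1.95 | 4.6% |
| 10% | 1.108 | 1.90 | 7.9% |

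For example, at f = 10%: 0.90 × 1.12 + 0.10 = 1.108, a shift of 0.012. At the margin, 0.90 × 2.0 + 0.10 = 1.90, and Φ(10.70 × ln(2/1.90) − 1.96) = Φ(−1.41) = 7.9%.

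**Effect on power of losing events.** With E replaced by (1 − f) × E and HR 1.12:

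| Share of events lost | Pooled power | Optum power |
|---|---|---|
| 0 | 0.99999 | 0.595 |
| 5% | 0.99998 | 0.573 |
| 10% | 0.99996 | 0.550 |
| 20% | 0.9998 | 0.503 |

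**Sensitivity to the matched total.** The Section 9 censoring table sums to 15,893 per arm, or 31,786 patients, not 32,998. That gives 31,786 × 13.87/1,000 = 440.9 events and power 0.99998, so the conclusion does not depend on which total is used.

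**The case against.** A reader might infer that all 19 codes are non-DVT admissions and that the hazard ratio is therefore biased toward 1. The documents do not support that.

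- **The direction is conditional.** Many of the labels are themselves venous thromboses, the kind of event that anticoagulants act on. If the drug contrast on them equals that on DVT and PE, there is no dilution. Nothing in the plan says how they respond.
- **Unspecified does not mean superficial.** The unspecified codes name no depth and may hold true DVTs. Code 453.8 is printed as the parent of 453.82 to 453.87, most of which name particular veins. Removing such codes from the primary outcome trades sensitivity for specificity, and the documents contain no validation data to settle the trade.
- **A rule that a label must name a deep limb vein is hard to apply evenly.** It would also question 453.2 (inferior vena cava), 453.86 (internal jugular) and 453.87 (other thoracic veins).
- **The share is probably limited.** Only inpatient primary-position diagnoses count. The Section 5.3 flowchart also excludes significant liver disease at baseline, which may reduce prevalent Budd-Chiari cases, though not new ones.
- **VTE is the protocol's own term.** Section 6.3.1 leaves its definition to Appendix A, so the list does not breach the protocol's definition.

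All of this stands, and it confines the point. It does not explain why Budd-Chiari syndrome and thrombophlebitis migrans sit under a DVT heading when the composite named in the same appendix is recurrent DVT or PE. Nor does it explain the lack of a narrower outcome against which to test the ambiguous codes.

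**Conclusion.** The concern holds in a limited form. Four codes (453 as Budd-Chiari, 453.1, I82.0, I82.1) do not belong to the composite being replicated and would score as recurrent VTE. The remaining 15 are ambiguous and may contain true DVT.

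Any pull toward 1 depends on these events responding less to the drug contrast than DVT and PE do. Its size depends on a share that the documents do not give. At the plan's assumed hazard ratio of 1.12 the shift is about 0.01 even at a 10% share, small beside the trial interval of 0.75 to 1.68 given in Appendix A. Error inflation becomes material only if the true hazard ratio is close to 2.0 and the share is several per cent: from 2.5% to 4.6% at 5%, or 7.9% at 10%. The documents do not show that the non-inferiority conclusion is unsafe. The case for acting is that the mismatch is plain and cheap to correct.

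**What to change.** 1. Remove Budd-Chiari syndrome (printed as 453; I82.0) and thrombophlebitis migrans (453.1; I82.1) from the primary outcome. Confirm how 453 was implemented: 453.4 and 453.5 are each printed twice with different labels, which suggests dropped trailing zeros, and 453 run as a prefix would take in every 453.x code.
2. Keep the unspecified and other-vein codes in the primary outcome.
3. Pre-specify in Section 13.2 a sensitivity outcome limited to PE and an explicit list of deep-vein codes, stating how 453.2, 453.86 and 453.87 are handled.
4. Report overall event counts under each definition, not split by treatment. This respects the bar in Section 7 on incidence rates by treatment group.

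The cost is a code-list edit and a rerun of overall counts and Section 10 power. The Section 12 and 13 dates are blank in this version, so the change can precede any dated treatment comparison. A few events are lost. Pooled power stays above 0.999 even at a 20% loss. Optum alone, already at 0.595, would fall slightly, to 0.573 at an assumed 5% loss.

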Appendix A

453.9

EMBOLISM AND THROMBOSIS OF UNSPECIFIED SITE

ICD-10 Dx inpatient primary position

PE

- I26.0 Pulmonary embolism with acute cor pulmonale
- I26.01 Septic pulmonary embolism with acute cor pulmonale
- I26.02 Saddle embolus of pulmonary artery with acute cor pulmonale
- I26.09 Other pulmonary embolism with acute cor pulmonale
- I26.9 Pulmonary embolism without acute cor pulmonale
- I26.99 Other pulmonary embolism without acute cor pulmonale

DVT

- I80.1 Phlebitis and thrombophlebitis of femoral vein
- I80.10 Phlebitis and thrombophlebitis of unspecified femoral vein
- I80.11 Phlebitis and thrombophlebitis of right femoral vein
- I80.12 Phlebitis and thrombophlebitis of left femoral vein
- I80.13 Phlebitis and thrombophlebitis of femoral vein, bilateral
- I80.2 Phlebitis and thrombophlebitis of other and unspecified deep vessels of lower extremities
- I80.20 Phlebitis and thrombophlebitis of unspecified deep vessels of lower extremities
- I80.201 Phlebitis and thrombophlebitis of unspecified deep vessels of right lower extremity
- I80.202 Phlebitis and thrombophlebitis of unspecified deep vessels of left lower extremity
- I80.203 Phlebitis and thrombophlebitis of unspecified deep vessels of lower extremities, bilateral
- I80.209 Phlebitis and thrombophlebitis of unspecified deep vessels of unspecified lower extremity
- I80.21 Phlebitis and thrombophlebitis of iliac vein
- I80.211 Phlebitis and thrombophlebitis of right iliac vein
- I80.212 Phlebitis and thrombophlebitis of left iliac vein
- I80.213 Phlebitis and thrombophlebitis of iliac vein, bilateral
- I80.219 Phlebitis and thrombophlebitis of unspecified iliac vein
- I80.22 Phlebitis and thrombophlebitis of popliteal vein
- I80.221 Phlebitis and thrombophlebitis of right popliteal vein
- I80.222 Phlebitis and thrombophlebitis of left popliteal vein
- I80.223 Phlebitis and thrombophlebitis of popliteal vein, bilateral
- I80.229 Phlebitis and thrombophlebitis of unspecified popliteal vein
- I80.23 Phlebitis and thrombophlebitis of tibial vein
- I80.231 Phlebitis and thrombophlebitis of right tibial vein

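### As printed, the primary VTE outcome differs between the ICD-9 and ICD-10 eras for vena cava and thoracic-vein thrombosis, and saddle PE is listed unevenly

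*Combined protocol and SAP*

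**What the plan says.** Sections 1.3 and 6.3.1 make VTE the primary outcome and leave its definition to Appendix A. There it is two lists of inpatient primary-position diagnoses, one per coding system.

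- **ICD-9, PE:** "415.1 PULMONARY EMBOLISM AND INFARCTION", then 415.11 and "415.19 OTHER PULMONARY EMBOLISM AND INFARCTION". No entry names a saddle embolus.
- **ICD-9, veins:** the list includes 453.2 ("EMBOLISM AND THROMBOSIS OF INFERIOR VENA CAVA") and 453.87 for other thoracic veins.
- **ICD-10, PE:** I26.0, I26.01, I26.02 ("Saddle embolus of pulmonary artery with acute cor pulmonale") and I26.09. Without cor pulmonale there are only "I26.9 Pulmonary embolism without acute cor pulmonale" and "I26.99 Other pulmonary embolism without acute cor pulmonale".
- **ICD-10, veins:** the I82 entries run I82.0, I82.1 and then I82.4 onward. Between I82.1 and I82.4 stands I80.3 ("Phlebitis and thrombophlebitis of lower extremities, unspecified"), which has already appeared a few lines above, before I80.9.

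Section 5.2.1 opens cohort entry in July 2011 for all three databases and closes it at the end of 2017 (Medicare), the end of 2018 (MarketScan) and in March 2020 (Optum). No section says whether a listed code matches only itself or also every code beneath it.

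**The concern.** The two lists should describe one endpoint in two coding systems. Where a site is counted in one and not in the other, an admission for the same event is an outcome or a non-outcome depending on which system was in force. Follow-up then mixes two definitions of the primary outcome, and rates are not comparable across calendar time.

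The saddle PE gap is different in kind. The trial endpoint that Appendix A reproduces counts all PE, fatal or not. The plan gives no reason for naming saddle emboli only when cor pulmonale is present, or for naming them in ICD-10 alone. If the codes are applied literally, a recurrent PE under its own saddle code would not be counted.

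**Working it through.** **1. The lists side by side (Appendix A).**

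| Site | ICD-9 | ICD-10 |
|---|---|---|
| Budd-Chiari | 453 | I82.0 |
| Thrombophlebitis migrans | 453.1 | I82.1 |
| Inferior vena cava | 453.2 | none |
| Lower-limb deep veins, acute | 453.4 to 453.42 | I82.4 family |
| Lower-limb deep veins, chronic | 453.5 to 453.52 | I82.5 family |
| Upper-limb deep, axillary, subclavian, jugular | 453.82, 453.84 to 453.86 | I82.62, I82.A1, I82.B1, I82.C1 families |
| Other thoracic veins | 453.87 | none |
| Other specified veins | 453.8, 453.89 | I82.890 |
| Saddle PE with cor pulmonale | no saddle entry | I26.02 |
| Saddle PE without cor pulmonale | no saddle entry | no saddle entry (I26.9, I26.99) |

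The lists otherwise track each other closely. The vena cava and thoracic-vein rows are the exceptions among the vein sites. The second I80.3 stands directly after I82.1, just as 453.2 stands directly after 453.1. That is what a data-entry slip would look like, though intent cannot be proved.

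**2. Does the matching rule matter?** For the vena cava and thoracic veins it does not. The ICD-10 list has no bare I82 and no parent between I82.1 and I82.4, so prefix matching has nothing to expand. If the printed 453 were itself a prefix, ICD-9 would become wider still and the gap would grow. For saddle PE the rule decides the matter: parents 415.1 and I26.9 are listed and would cover any code beneath them under prefix matching, but not under exact matching.

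**3. The plan's own power figures (Section 10).** Inputs: HR 1.12, margin 2.0, two-sided alpha 0.05, and events d = matched patients × risk per 1,000 / 1,000. Formula: power = Φ(√(d/4) × [ln 2.0 − ln 1.12] − 1.96), with ln 2.0 − ln 1.12 = 0.5798.

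- Pooled: d = 32,998 × 13.87/1,000 = 457.68. √(457.68/4) = 10.697, and 10.697 × 0.5798 − 1.96 = 4.24, so power is 0.99999 (stated 0.999988934).
- Optum: d = 57.57, power 0.5947 (stated 0.594735156).
- MarketScan (0.9647) and Medicare (0.9932) also reproduce.

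**4. Power if codes are added.** There are no code-level counts, so let s be the share of true VTE admissions that fall only under unlisted codes. The assumed range is 1% to 20%. If the risks in Section 10 come from the printed list, missed events are additional to d, and the completed count is d/(1 − s).

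| | s = 0 | s = 1% | s = 20% |
|---|---|---|---|
| Pooled events | 457.7 | 462.3 | 572.1 |
| Pooled power | 0.99999 | 0.99999 | above 0.9999 |
| Optum power | 0.595 | 0.599 | 0.691 |
| MarketScan power | 0.965 | 0.966 | 0.988 |
| Medicare power | 0.9932 | 0.9936 | 0.9986 |

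**5. Power if 453.2 and 453.87 are dropped.** Events fall. Pooled power of 0.9999 needs √(d/4) × 0.5798 = 3.719 + 1.960 = 5.679, so d = 4 × (5.679/0.5798)² ≈ 384. The pooled count could lose about 74 of 457.7 events (16%) before going below 0.9999.

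**6. Hazard ratio.** For a rare event, observed HR ≈ true HR × (capture with rivaroxaban / capture with warfarin). Equal capture gives a ratio of 1 and no change. Illustrations only: 1.12 × 0.95/1.00 = 1.06, and 1.12 × 0.95/0.90 = 1.18. Both are far from 2.0, and the documents give no figure for either capture.

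**The case against.** The strongest reply concerns saddle PE. Both parent codes are on the list, no matching rule is given, and Appendix A elsewhere uses category-level codes without children, such as 660 in the pregnancy list. On that reading nothing is lost. Nor can the documents confirm that a separate saddle code exists in ICD-9 or under I26.9. This stands in part: a loss of saddle PE cannot be asserted as fact. The layout nonetheless points toward exact codes. The printed 453 is labelled as Budd-Chiari alone, which as a prefix would swallow every other 453 line. Children are spelled out beneath their parents, and the numbering jumps from 453.8 to 453.82 and from the I82.60 group to I82.62. The repeated 453.4 and 453.5 suggest lost trailing zeros, so the print is not a fully reliable guide to what was run.

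A second reply is that the residual entries I82.890 or I82.90 might collect vena cava and thoracic-vein events. The documents do not say so, and the ICD-9 list carries its own residual code (453.89) alongside the specific ones. This is a matter for the code-set check.

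A third is that these venous sites may not belong in a recurrent DVT or PE endpoint at all. That is a legitimate choice, but it has to be the same in both eras.

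A reader might go further and infer that the most severe recurrences go uncounted, or that the loss favours rivaroxaban because its use came later. The documents support neither. I26.0, I26.01, I26.02 and I26.09, all with cor pulmonale, are listed. No entry dates by arm are given. Longer prior database time for rivaroxaban in MarketScan before matching (2,057 v 1,771 days) is compatible with later entry but does not show it, and it is nearly equal after matching (2,044 v 1,984). The legible part of Appendix B does not settle whether calendar time is in the propensity score.

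**Conclusion.** The point holds as one of endpoint consistency. The printed primary outcome counts inferior vena cava and other thoracic-vein thrombosis under ICD-9 and has no corresponding entry or parent under ICD-10, whichever matching rule applies. The uneven treatment of saddle PE is visible on the page; whether it loses events depends on the unstated matching rule and on the code set.

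Neither the number of missed events nor the direction of any bias can be derived. Under-capture equal in the two arms leaves the HR about unchanged. Pooled power stays above 0.9999 across the assumed 1% to 20% omission, and would do so after dropping the two ICD-9 codes unless they carry more than about 16% of events. Optum alone is at 0.595 for reasons unrelated to this point. Correction is worthwhile because it makes the primary endpoint one definition throughout, not because the non-inferiority conclusion is shown to be at risk.

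**What to change.** 1. Make the vein lists correspond. Either replace the duplicate I80.3 with the ICD-10 codes for vena cava and other thoracic-vein thrombosis, or drop 453.2 and 453.87.
2. Add the saddle PE codes in both systems after checking them against the official code set.
3. State in Appendix A whether codes match exactly or by prefix, and restore any trailing zeros lost in the printed list.
4. Tabulate outcome events by code and by coding era, pooled across arms, before the comparative analysis.

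The cost is a code-list edit and a rerun of the outcome query; no patients are lost. Section 13 records no date for the comparative analyses, so on the face of the document the change can still be made without knowledge of treatment results. Made afterwards, the same edit could look outcome-driven.
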